Protocol & SAP

Airways to Alteration (A2A): Investigating the Impact of Breathwork & Meditation on Conscious State (NCT06916312)

Comparing Effects of Intense Breathwork to Meditation on Altered States of Consciousness (A2A)

Summary

This study aims to investigate the impact of high ventilation breathwork (HVB) and meditation on altered states of consciousness (ASCs). The study will compare the effects of a single guided HVB session to a single guided body scan meditation session. The primary aim is to explore the impact of HVB and meditation on ASCs, while secondary aims relate to mental health and wellbeing.

[name]

Original document date: May 21, 2025

Edited document data: June 09, 2025

Reason for edit: Had EBI listed as secondary outcome measure (incorrect) in the Protocol instead of a primary outcome measure (correct) as per the pre-registration NCT06916312.

Abstract

Breathing is fundamental to life, rooted in the Latin word "spiritus," meaning spirit or life force. Through this project, we aim to explore the impact of high ventilation breathwork (HVB), a practice that uses deliberate, intensified breathing to create altered states of consciousness (ASCs). These states have been described as lived experiences that expand perception, foster a sense of connection, and bring deep personal insights. While substances like psychedelics are known to induce ASCs, they are often restricted due to costs, legal limitations, and health concerns. HVB, however, offers an accessible, drug-free way to reach similar states. Early research even suggests that HVB can lead to experiences comparable to those produced by medium-to-high doses of certain psychedelics, like psilocybin. Yet, unlike meditation or other therapeutic practices, HVB has not been rigorously studied in clinical trials. Our study plans to take an important first step by conducting a randomised controlled trial (RCT) on the effects of a single guided HVB session. This will involve experienced breathwork practitioners and will assess a range of outcomes, including ASCs, mystical experiences, emotional breakthroughs, and overall mental wellbeing. To help us understand the unique effects of HVB, we will also have a comparison group, where participants will engage in a meditation session led by the same facilitator. Essentially, we will be comparing a single guided session of HVB (intervention) to a single guided session of body scan meditation (active comparator). Then, using the Altered States Database, an open-science project based on systematic literature reviews, we can compare to prior data on altered state-induction methods like meditation and psychedelics. The primary aim is the impact of HVB and meditation on ASCs. Secondary aims relate to mental health and wellbeing. For the first time we will also examine the relationship between predictiveness of the psychedelic experiences emerging from HVB and meditation. By conducting this study, we hope to create a foundation for future clinical research and build evidence on HVB's potential as a therapeutic tool. This project responds to the growing interest in non-drug methods for achieving profound mental and emotional states—showing that the key to these transformative experiences may be as close as our own breath.

Introduction

High ventilation breathwork (HVB), mind-body practices which increase respiratory rate and/or depth, has been used to relieve various forms of psychological distress for millennia. Recently HVB has started receiving an unprecedented surge in public interest owing to its potential to induce altered states of consciousness (ASCs) and improve mental/physical health. Psychoactive substances represent one way to evoke ASCs but unquestionably not the only one[1]. Whilst there has been an explosion in psychedelic research in the West, ancient cultures across the globe have used physical challenges to evoke ASCs in ceremonial settings, i.e., extreme temperatures, fasting and sleep deprivation. However, arguably the most accessible of which is HVB—techniques that are observed worldwide and have complex historical roots grounded in both religious and secular traditions [2]. Such practices have been used since time immemorial for spiritual and healing purposes, being frequently described in the rituals of many cultures [2]. We aim to meticulously explore the phenomenological effects of HVB. With thoughtfully curated set and setting, HVB has been reported to elicit profound mystical experiences and ASCs akin to those evoked by psychedelics [1,3], including medium to high doses of psilocybin [4]. Current research on ASCs has predominantly focused on pharmacological methods, however there is a growing interest in nonpharmacological approaches, which are often more accessible and culturally acceptable. This also removes medical, legal and financial barriers [1].

Our Lab has started characterising phenomenological and neurophysiological effects of HVB to inform its mechanism of therapeutic action, safety profile and future application. Clinical observations and data from neurophysiological studies indicate that HVB is associated with extraordinary changes in subjective experience, and profound effects on central and autonomic nervous systems functions through modulation of neurometabolic parameters and interoceptive sensory systems [2]. Nondrug alternatives for eliciting and working with ASCs are needed, as many individuals wish to derive therapeutic benefit via experiencing psychedelics' effects without the need to ingest substances. Breathing provides a potential resource that we have at our disposal (here and now) for improving wellbeing, and its consciousness expanding effects can be stopped at any point by simply returning to a normal cadence. With HVB we are not solely relying on an external source in the form of a drug compound, but our own innate inner capacity for healing. However, like psychedelics, as HVB becomes increasingly popular, it is extremely important that the hype is grounded in—and calibrated with—robust research evidence. This translates to rigorous clinical testing.

The study is a randomised controlled trial (RCT) involving up to 24 healthy adult participants who have prior experience with HVB. Participants will be randomly allocated to either the HVB or meditation group. The study will assess outcomes such as ASCs, mystical experiences, emotional breakthroughs, psychological insight, and overall wellbeing.

Motivation

Despite ancient and modern use paired with countless anecdotal evidence of its profound effects, empirical research on HVB is limited [2]. No published study has yet examined the effects of HVB on ASCs through an RCT. To put the ASC field in perspective, only data from one published HVB study [3] are currently listed on the Altered States Database* [5] (an open-science project based on systematic literature reviews) for an established psychological measure of ASCs, in comparison to 40 and 44 entries on psilocybin and LSD, respectively. Moreover, there are no published data on HVB for an established psychological measure of mystical experiences on the Altered States Database, but there are 33 and 23 entries for psilocybin and LSD, respectively. Most breathwork research at present has been on slow-paced techniques [6,7], however the field of HVB is currently in its infancy [2,8].

**The database is powered by the Collaboration for Interdisciplinary Research on Conscious Experiences (CIRCE).*

Impact/Significance

Such (breath)work has the potential of helping pioneer a new therapeutic modality in the form of the breath, a tool which can be accessed by anyone instantaneously. This may pave the way for larger, robust RCTs on HVB to occur. In doing so, at a societal level, we could help establish HVB as an accessible, low-cost nondrug alternative for expanding global consciousness. Large-scale robust clinical testing is a necessary step for the evolution of HVB if it is to be integrated into healthcare systems across the world. The perturbed psychophysiological state induced by HVB may also have broader applications regarding how it can be harnessed in a therapeutic context. Deeper knowledge of the ASCs induced by HVB—through rigorous testing of its effects—may deliver societal benefit, in a time where raising global consciousness is needed most. This research represents a step to doing just that.

Research Aims/Questions

Principal research questions/objectives include: 1. Investigate potential differences in ASCs induced by a single session of HVB—in particular Conscious Connected Breathing (CCB)—versus a body scan meditation. 2. Examine whether HVB (CCB) induces ASCs comparable to psychedelics (via the Altered States Database, an open-science project based on systematic literature reviews). 3. Investigate potential differences on mental health and wellbeing after HVB or a body scan meditation. 4. Examine correlation between ASCs and changes on mental health and wellbeing, in addition to the relationship between preparedness/predictiveness of participants to experience psychedelic effects and ASCs.

Materials/Methods

Unlike slow breathwork, high ventilation breathwork (HVB) has not been exposed to the same level of robust clinical testing to date [2,6-8], a necessary step to realise its potential application as a therapeutic modality. We will conduct the first randomised-controlled trial (RCT) of HVB on altered states of consciousness (ASCs). This will take the form of a small pilot study wherein participants are randomised to in-person, guided HVB or a meditation group.

Study type

This will be an experimental study, where participants are randomly assigned to a HVB intervention or body scan meditation. This will be a small-scale pilot RCT, hopefully leading to a large-scale clinical trial in the future (depending on funding).

Data collection procedures

Quantitative data: The primary outcomes will be ASCs as measured by the Five Dimension ASC Rating Scale (5D-ASC) [9], the short Mystical Experience Questionnaire (MEQ) [10], and Emotional Breakthrough Inventory (EBI) [11].

Secondary outcomes include: the Psychological Insight Questionnaire (PIQ) [12], Depression Anxiety Stress Scales (DASS) [13], Short Warwick-Edinburgh Mental Wellbeing Scale (SWEMWBS) [14], Imperial Psychedelic Predictor Scale (IPPS) [15], PROMIS Sleep-Related Impairment Scale (PROMIS-4a) [16], Shortened Fatigue Questionnaire (SFQ) [17], and Cambridge Depersonalisation Scale-State Version (CDSS) [18].

There will also be optional open-ended responses on overall experience of the meditation or breathwork. The following state measures will be completed immediately after the HVB and meditation sessions: 5D-ASC, MEQ, EBI and CDSS. The following trait measures will be completed 7-10 days before and 7-10 days after the breathwork and meditation sessions: DASS, SWEMWBS, PROMIS and SFQ. The IPPS will be completed when subjects consent to participating, and the PIQ will be completed 7-10 days after the breathwork and meditation sessions.

Qualitative data: Optional open-ended responses will capture participants' lived experiences after the breathwork and meditation sessions.

Sample

Given this is a small pilot study, 24 participants (12 per group) will be recruited. The studies of Bahi et al. (2023) and Havenith et al. (2024) report HVB having comparable effects on ASCs to moderate-high doses of psilocybin, which has large-very large effect sizes on ASCs. This is an ethical number of participants for a single session HVB intervention with two breathwork facilitators present. It is ideal to have no more than six breathworkers per facilitator.

Accordingly, there will be two groups of 12 for our study (12 in the HVB group, and 12 in the meditation group). At 80% power with an alpha of 0.05, based on Havenith et al.'s HVB study's between-groups effect size (1.29) on the self-completion depressive symptomology survey, a sample size of 22 is needed, allowing room for potential attrition. Effect sizes reported by Bahi et al. were greater, but this was a within-groups design.

Participants will be recruited from the local area using advertisements online (social media/email) via the PI and (co)facilitators' networks. It will be incumbent upon those people interested in taking part to contact the PI. Participants will be comprehensively screened and the inclusion criteria will be adults with experience of HVB, living in Brighton (UK) and the surrounding area. Given the nature of HVB, the comprehensive eligibility criteria are as follows:

Inclusion Criteria: Healthy adults (18-65) in Brighton and the surrounding area; Prior experience practising high ventilation breathwork in the form of conscious connected breathing; No history of adverse events during such prior breathwork sessions. *Exclusion Criteria:* History of hypotension; Hypertension; Respiratory or cardiovascular problems; Fainting or syncope; Epilepsy or seizures; Panic disorder or panic attacks; Cerebral aneurysm; Pregnancy (and possibility one might be pregnant, trying to get pregnant, or are breastfeeding); Breathlessness; Bradypnea; Tachypnoea; Any mental/physical issues affecting the ability to engage in breath control activities.

Procedure

Prospective participants will be emailed an Information Sheet—and they will be given as long as needed to decide if they wish to participate. A Consent Form will be completed prior to any study related procedure. The informed consent process will include aims, rationale, methods and potential adverse effects of the study and will be followed by the completion of the Consent Form. The participant will be allowed as much time as they wish to consider the information, and the opportunity to question the PI, their GP, or any other independent parties to decide whether they will participate in the study. The PI taking consent will explain to the potential participants that they are free to refuse any involvement within the study or alternatively withdraw their consent at any point during the study—for any reason. The informed consent of the participant will be recorded and retained using an online form, with a copy of the signed Consent Form of which they can keep. No study procedure will be carried out until informed consent has been obtained from the participant.

Participants will be able to withdraw from the study at any time, and for any reason, without having to provide any explanation for their decision. Participants will be told that they can withdraw from the study at any time. If they request it, their data can be removed from the database. The deadline for the withdrawal of their data will be at the time of completion of data analysis. We expect this to be around 3 months after the session.

Participants will be briefly screened for eligibility prior to taking part into the study. They will be randomly allocated to HVB or meditation groups using block randomisation (1:1), stratified by scores on the brief 9-item Imperial Psychedelic Predictor Scale (IPPS), which will be completed shortly after the Consent Form has been signed. Short self-completion questionnaires will be administered to participants ~1 week pre and post the HVB or body scan meditation, along with once immediately after the HVB and meditation. The platform used for questionnaires will be Qualtrics and, where visual analogue scales are used, will contain a scale with 0 (%) on the left and 100 (%) on the right. The single sessions of breathwork and meditation will take place at Little Dippers in Brighton, a naturalistic setting where the facilitator regularly teaches HVB.

Participants will be compensated 5GBP, 10GBP and 15GBP (money) per questionnaire completed (30GBP total but in a phased manner to increase retention). Moreover, participants, regardless of group, will be participating in an active intervention (HVB or body scan meditation) which will be provided free of charge.

Processing and Analysis Plan

Results will be analysed using the software programme *R*. The outcome measures collected on the day of the HVB or meditation will be analysed using simple quantitative analyses (i.e., unpaired t-test or Mann-Whitney U-test depending on distribution of the data), whilst the outcomes ~1-week pre-post will be analysed using repeated-measure analysis of variance (ANOVA) or Friedman's test depending on distribution of the data. Changes on the mental health and wellbeing measures will be correlated with scores on the ASC measures. Simple qualitative content analysis will be used to analyse any responses to open-ended questions of participants' experience of the HVB or meditation.

Ethical considerations

The Brighton and Sussex Medical School Research Governance and Ethics Committee (RGEC) has assessed this project and granted Ethical and Research Governance Approval to proceed (Reference Number: ERA/GF221/9/1).

References

1. Havenith, M. N., Leidenberger, M., Brasanac, J., Corvacho, M., Carmo Figueiredo, I., Schwarz, L., ... & Jungaberle, A. (2025). Decreased CO₂ saturation during circular breathwork supports emergence of altered states of consciousness. *Communications Psychology*, 3(1), 59.

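### No adverse-event or early-stopping record and no harms report by arm is specified, although eligibility and consent treat adverse effects of HVB as real

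*Combined protocol and SAP*

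**What the plan says.** **Eligibility and consent.** The inclusion criteria under Sample require "No history of adverse events during such prior breathwork sessions". The exclusions that follow include fainting, seizures, panic, and cardiovascular or respiratory problems. Under Procedure, "The informed consent process will include aims, rationale, methods and potential adverse effects of the study".

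**Data collection procedures.** The 5D-ASC, MEQ, EBI and CDSS are completed straight after the session. DASS, SWEMWBS, PROMIS and SFQ are completed 7-10 days before and 7-10 days after it. The PIQ is completed only at the later time point, and the IPPS at consent. The section adds: "There will also be optional open-ended responses on overall experience of the meditation or breathwork".

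**Processing and Analysis Plan.** Day-of-session scores are compared by unpaired t-test or Mann-Whitney test, and pre-post scores by repeated-measures ANOVA or Friedman's test. Changes on the mental health and wellbeing measures are correlated with the ASC scores, and free text receives a simple content analysis.

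No section defines an adverse event, asks about one, sets a window or recording route, records whether a participant stopped the session early, or plans a table of harms by arm. Adverse events or effects are mentioned only twice, in the eligibility criteria and in the consent procedure.

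**The concern.** The plan recognises specific events closely enough to exclude people prone to them, then provides nowhere to write them down if they occur. The Introduction says the effects of HVB can be ended at any time by going back to normal breathing, but nothing records whether anyone did so. Participants may also withdraw without giving a reason and have their data removed. That right is proper, but with no question about unwanted effects, someone who leaves after a bad reaction may leave no trace in the report.

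What is at stake is descriptive information. The trial is presented as a pilot for larger trials of HVB, and the planners of such trials will want counts of unwanted effects in both arms, obtained in the same way. Events that nobody asks about at the time cannot be reliably reconstructed at the analysis stage.

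**Working it through.** **1. Arm size.** The Sample section states: "Given this is a small pilot study, 24 participants (12 per group) will be recruited". Its calculation is given as "At 80% power with an alpha of 0.05", with a "between-groups effect size (1.29) on the self-completion depressive symptomology survey, a sample size of 22 is needed". A two-sided two-sample t-test (noncentral t, standardised difference 1.29) has power 0.779 with 10 per arm and 0.821 with 11 per arm, so 11 per arm, or 22 in total, is reproduced. With 12 per arm the power is 0.855. This figure does not bear on harms; it only confirms the arm size of 12 used below.

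**2. What each planned item could show.**

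| Item (both arms) | When | Could show | No field for |
|---|---|---|---|
| CDSS | Straight after the session | Depersonalisation | A faint, a panic reaction, stopping early |
| DASS | 7-10 days before and after | Change in depression, anxiety, stress | A discrete event on the day |
| PROMIS | Same | Change in sleep-related impairment | Same |
| SFQ | Same | Change in fatigue | Same |
| Free text (optional) | After the session | Whatever is volunteered | A count: silence does not mean absence |

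**3. One affected participant in a comparison of averages.** If one of 12 participants worsens by k standard deviations and nobody else changes, the arm mean moves by k/12 SD. The standard error of a difference between two arms of 12 is √(1/12 + 1/12) = 0.408 SD. To move the difference by just one standard error, k would have to be 0.408 × 12 = 4.9. This ignores the rise in the SD that such an outlier would cause, which would hide it further. The rank tests also give a single participant little weight.

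**4. What solicited counts would show.** The documents give no event rate, so the true risks p below are assumptions. The chance of at least one event in 12 is 1 − (1 − p)^12.

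| Assumed p | Calculation | Chance of at least one event |
|---|---|---|
| 1% | 1 − 0.99^12 | 11% |
| 5% | 1 − 0.95^12 | 46% |
| 10% | 1 − 0.90^12 | 72% |
| 20% | 1 − 0.80^12 | 93% |

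With no events in 12:
- One-sided 95% upper limit: 1 − 0.05^(1/12) = 22.1%.
- Upper limit of the exact two-sided 95% interval: 1 − 0.025^(1/12) = 26.5%.
- With 11 in the arm, the same limits are 23.8% and 28.5%.

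**5. Why no test.** Against 0/12 in the other arm, the two-sided Fisher p-value is 0.093 for 4/12 and 0.037 for 5/12. Only a very large imbalance would reach the 5% level, so a non-significant result would say almost nothing.

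**The case against.** The strongest case on the other side is that unwanted effects have several ways to come to light.

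- CDSS, DASS, PROMIS and SFQ are structured, given in both arms, able to worsen as well as improve, and secondary outcomes with a planned analysis. The last three have a baseline and would pick up some delayed problems.
- Sessions are in person, and the Sample section describes two facilitators at the HVB session, so an acute event would probably be witnessed.
- Safety is not among the objectives under Research Aims/Questions.
- The ethics application and information sheet are not among the documents, consent pages were removed from the text, and the list of secondary outcomes is worded as an inclusion rather than an exhaustive list.

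Most of this stands, and it rules out several stronger readings that a reader might infer:

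- *Harms can surface only through free text.* The scales and the facilitators contradict this, and no section assigns harms to the free-text item.
- *Only benefits can be reported.* The four scales can be compared by arm, though as symptom scores rather than events.
- *The trial fails a safety aim of its own.* The Introduction's phrase "to inform its mechanism of therapeutic action, safety profile and future application" describes the research group's wider programme, not this trial's objectives.
- *Counts from this sample would understate risk in first-time users.* This is plausible, because participants must have prior experience without adverse events, but the documents contain no data on it.

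The objection does not supply a recording route. A witnessed faint still has no form and no line in the report, and mean scores cannot be turned into event counts.

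**Conclusion.** The point holds as a modest one: this document does not specify adverse-event or early-stopping collection, or harms reporting by arm, and the scales it does collect are not designated for safety. It would go too far to say that the investigators have no such procedures, since these may sit in the ethics application.

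The change is worth making because it alters what is collected, not just how it is described. The gain is limited. With 12 per arm, a risk of 1% or 5% would more often than not go unseen, and an empty cell would still be compatible with a risk above 20%. The 1% to 20% risks are assumptions, and the calculations take every participant in the arm to answer the question. Any counts would describe people with uneventful prior experience of HVB. The primary outcomes and their analysis are not affected.

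**What to change.** **Collection, both arms**
- Add a mandatory yes/no item on unwanted effects, with a description if yes, to the immediate post-session form and to the 7-10 day form.
- Add an item to the immediate form asking whether the participant stopped the session early.

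**Reporting**
- Give counts by arm with exact 95% confidence intervals and no hypothesis test, stating how many participants answered.
- Describe individual worsening on CDSS, DASS, PROMIS and SFQ by arm alongside the planned group comparisons. CDSS has no baseline, so for that scale show the individual post-session scores.

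**Cost.** Two or three extra items on Qualtrics forms that both arms already complete, one descriptive table, and possibly an update to the ethics approval. If the ethics application already contains adverse-event procedures, align the items with them, refer to them in this document, and add the table.

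### Each arm appears to be one group session of 12, so session and arm cannot be separated, and the plan does not limit Objective 1 to the two sessions held

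*Combined protocol and SAP*

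**What the plan says.** The Sample section ties the arm size to delivery. It calls the number of participants ethical for a "single session HVB intervention with two breathwork facilitators present", adds "It is ideal to have no more than six breathworkers per facilitator", and concludes that "there will be two groups of 12 for our study".

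For the comparator, the Abstract says "participants will engage in a meditation session led by the same facilitator". The Procedure section begins its sentence on the venue with "The single sessions of breathwork and meditation will take place" and names one site for both. No sentence gives the number of sittings per arm.

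Participants are randomised individually, 1:1 in blocks, stratified by IPPS score (Procedure). The three primary outcomes (5D-ASC, MEQ and EBI) are completed straight after the session. The Processing and Analysis Plan compares outcomes from that day by an unpaired t-test or a Mann-Whitney test, with no term for session. Objective 1 under Research Aims/Questions is to "Investigate potential differences in ASCs induced by a single session of HVB", specifically conscious connected breathing (CCB), against a body scan meditation.

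**The concern.** If the 12 members of an arm attend together, whatever is particular to that sitting is shared by the whole arm and absent from the other: the mood of the group, one participant's strong reaction, how the facilitation went that day. Individual randomisation balances who attends each session, but not what happens in the room. The primary outcomes are self-rated directly after the shared experience, when some similarity between session-mates is plausible.

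Objective 1 is worded for the two methods, and the plan nowhere restricts it to the sessions held. A significant primary result could therefore be read as an effect of CCB when part of it belongs to these two sittings.

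**Working it through.** **Inputs from the document.** 12 per arm, effect size 1.29, alpha 0.05, power 80%, required total 22 (Sample); unpaired t-test (Processing and Analysis Plan).

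**Assumptions.** Two-sided alpha. The document gives no ICC, so 0.01, 0.05 and 0.10 are used as illustration.

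**1. The plan's own figure.** A two-sample t-test at d = 1.29 has power 77.9% with 10 per arm and 82.1% with 11. So 11 per arm, 22 in total, reproduces the plan exactly; 12 per arm gives 85.5%. All of this treats participants as independent.

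**2. Number of sessions.** 2 facilitators x 6 = 12 = one arm. The facilitator ceiling explains an arm of 12 only if the arm attends together.

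**3. Degrees of freedom for session.** With k sessions per arm, df = 2k - 2. For k = 1, df = 0. Variation between sessions cannot be estimated from these data, and this result needs no ICC.

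**4. Equal session variance in both arms.** With total variance s²:
- True variance of the mean difference: 2s²(1 + 11·ICC)/12.
- Variance that the t-test estimates: 2s²(1 - ICC)/12.
- Inflation of t: f = sqrt[(1 + 11·ICC)/(1 - ICC)].
- Error for inference beyond the two sessions: P(|T| > 2.074/f) on 22 df.

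**5. Session effects in HVB only.** With the same within-session variance in both arms, the true variance is s²·ICC + 2s²(1 - ICC)/12, so f = sqrt[1 + 6·ICC/(1 - ICC)].

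| Assumed ICC | f, both arms | Error | f, HVB only | Error |
|---|---|---|---|---|
| 0.01 | 1.059 | 6.3% | 1.030 | 5.6% |
| 0.05 | 1.277 | 11.9% | 1.147 | 8.4% |
| 0.10 | 1.528 | 18.8% | 1.291 | 12.2% |

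By simulation, the exact Mann-Whitney test in the equal-variance case gives 5.7%, 10.7% and 17.1%.

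**6. Effect of the IPPS strata.** The t-test ignores the strata, which makes it conservative if they predict the outcome. The number of strata is not given. A simulation with two strata balanced 6/6 in each arm and equal session variance gives:
- strata explaining 10% of within-session variance: about 5.1%, 10.6% and 17.8%;
- strata explaining 20%: about 4.0%, 9.4% and 16.5%.

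At ICC 0.01 the excess can therefore vanish.

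**7. ICC at which significance is lost.** Setting f = t/t_crit in step 4 and writing r = (t/t_crit)² gives ICC = (r - 1)/(n - 1 + r). With n = 12 and t_crit = 2.074:
- Observed 1.0 SD: t = 1.0 x sqrt(6) = 2.45, r = 1.395, ICC = 0.395/12.395 = 0.032.
- Observed 1.29 SD: t = 1.29 x sqrt(6) = 3.16, r = 2.321, ICC = 1.321/13.321 = 0.099.

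Under step 5 the formula becomes (r - 1)/(5 + r), giving 0.395/6.395 = 0.062 and 1.321/7.321 = 0.18. The figure depends on where session effects are assumed to arise and must be labelled accordingly.

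**The case against.** The layout is inferred. The document also uses a single session to describe the dose each participant receives, and the ceiling of six per facilitator is only called ideal. Several sittings per arm are not excluded, and for meditation the evidence is wording alone. This stands, and it is why the first request is to state the number of sittings.

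The study calls itself a small pilot, and Objective 1 speaks of investigating potential differences. The Impact/Significance section says "This may pave the way for larger, robust RCTs on HVB to occur" and treats large-scale testing as still necessary. A reader might infer from that section that the plan already claims a general effect of HVB. It does not support that reading; if anything it points to caution. What remains is that no sentence confines the primary comparison to the sessions held, while the plan powers a between-groups test at alpha 0.05.

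The common facilitator, the single venue and the requirement of prior CCB experience may keep session variation small. They cannot remove it, and the trial cannot show that it is small.

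The error rates rest on assumed ICCs and on assumptions about session variance and strata. That also stands. Only the 0 degrees of freedom is free of assumption.

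**Conclusion.** The point holds as a limit on inference that the plan should state. If each arm is one sitting, session and arm are inseparable whatever the p-value, and the planned test supports a difference between these two sessions rather than between CCB and body scan as methods. For the wider reading, the nominal 5% error lies between 5.6% and 18.8% over ICC 0.01 to 0.10 and the two session-variance cases without a strata effect. It is lower if the IPPS strata matter, and can fall to 5% or below at ICC 0.01.

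Three stronger readings are tempting but unsupported:
- That the primary test is wrong. It is reasonable for the two sessions as delivered.
- That the sample size is miscalculated on its own terms. It reproduces exactly.
- That the true error is known to be 12% or 19%. The document gives no ICC, so these are illustrations.

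Nor would staying significant up to some chosen ICC justify the general claim. Any such ceiling is arbitrary: at ICC 0.20 the equal-variance error is 31.1%.

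**What to change.** 1. State the number of sittings planned per arm.
2. If it is one, keep the planned test and state unconditionally that session and arm cannot be separated and that the primary results are a difference between these two sessions.
3. For each significant primary t-test, report the ICC at which significance would be lost: (r - 1)/(n - 1 + r), with r = (t/t_crit)², n the harmonic mean of the arm sizes and t_crit on the actual degrees of freedom. Label it as descriptive and as assuming equal session variance. It is not a pass/fail rule. If the Mann-Whitney test is used, item 2 applies without this figure.
4. If several sittings are held, report results by sitting and name session as a limitation.

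The cost is a few lines of text and a more cautious conclusion. No new data, participants, sessions or staff are needed. Splitting the same 24 into two sessions of six per arm is not a cheap alternative for a formal test: it leaves 2 degrees of freedom for session and about 42% power at 1.29 in a session-level test even at ICC 0. That effect size also comes from a depression survey, not from a primary outcome.
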